## 2.3. Study Design

Overview of Study Design and Key Features	
Design Features	
 
Multi-centre, prospective, observational cohort study (registry).
 
Subjects receiving or initiating BENLYSTA and/or other immunosuppressant SLE medications (e.g. azathioprine, methotrexate, cyclophosphamide, mycophenolate, and biologics) (all medication decisions are at the discretion of the subject and their healthcare provider, and are not mandated by study design or protocol).
 
Subjects are followed-up approximately every 6 months for 5 years for occurrence of AESI (primary endpoint) and assessment of secondary endpoints including SDI organ damage.
 
Assessments are intended to be performed every 6 months based on information gathered during routine care and hospital attendance as there are no protocol mandated study visits*
 

Time & Events	Appendix 1: Schedule of Activities provides details of study activity timelines and data collection.
Exposure Assignment	
 
No formal or protocol defined treatment assignment.
 
Subjects are enrolled into 1 of 2 exposure groups; those who, at baseline, are receiving or initiating BENLYSTA (BENLYSTA or Exposed group) or are not receiving BENLYSTA (Non-BENLYSTA or Unexposed group).
 

Interim Analyses	
 
Annual interim analyses were planned throughout the study life cycle until the end of study in 2025. The interims were done for monitoring the safety of BENLYSTA and for reporting study progress to the external Scientific Advisory Committee, Benlysta Safety Review Team and Regulators.
 

Final Analysis	
 
Final analysis is planned for 2025 such that the enrollment and 5-year follow-up of every subject will have been completed.
 

\* Study setup to collect data during routine visits at approximately 6-month intervals  $\pm$  2months; this data collection interval is intended to align with routine standard of care visits for SLE subjects.

## 2.4. Statistical Hypotheses / Statistical Analyses

The purpose of the study is to evaluate the incidence of AESI over 5 years in adults with SLE being treated with and without BENLYSTA in a real-world setting. No formal statistical hypotheses testing will be conducted since there is no pre-specified hypothesis for any of the study endpoints.

Unless otherwise specified, the following measures will be used:

- Categorical variables will be summarized as the number of subjects and percentages (%) of subjects in each category. Percentages will not include the missing category and will be calculated over the number of subjects with available (non-missing) data.
- Continuous variables will be summarized using the mean, standard deviation (SD), median, first and third quartiles (Q1, Q3), minimum (min), maximum (max).
- Computed percentages will be presented with one decimal place. Percentages equal to 100 will be presented as 100% and no percentage will be presented for zero frequencies. In case of presenting CIs for categorical/qualitative data, exact methods for deriving these intervals will be used in case of descriptive statistics.
- The 95% CI will be computed for rates to contextualize the extent of random error but will not be used for formal statistical hypothesis testing.

### **3. PLANNED ANALYSES**

#### **3.1. Interim Analyses**

Annual interim analyses were conducted throughout the study life cycle at a prospectively pre-determined data cut-off date until end of study reporting in 2025 for the monitoring and reporting of study progress to either the external Scientific Advisory Committee, Benlysta Safety Review Team and/or regulators.

#### **3.2. Final Analyses**

The final planned analyses will be performed after the completion of the following procedure:

1. All subjects have completed their 5-year follow-up (or early withdrawal assessment for subjects withdrawing prior to completion of the 5-year follow-up), i.e. the last subject last visit milestone.
2. All required database cleaning activities have been completed and final database lock (DBL) has been declared by Data Management.

Further details of the sequential steps above, along with the relevant timelines can be found in the Clinical Study Activity Plan (CSAP).

This RAP describes the planned statistical analyses to be conducted for the final reporting. The AE review/categorization process is detailed in Appendix 3 (Section 9.3). The descriptive summary of baseline characteristics will be produced by exposure group (i.e. Benlysta or Exposed vs Non-Benlysta or Unexposed) using the 'Eligible' analysis population (see Section 4). A separate descriptive summary may be produced for the two study cohorts ('Current Users' and 'Treatment Initiators', see Section 5.6.2).

Safety and effectiveness endpoints will be analysed using the 'Evaluable' population. Results will be summarized by subjects' exposure group (i.e. Benlysta or Exposed vs Non-Benlysta or Unexposed) defined using the 'Initial Exposure', 'Ever-Exposed', and/or 'As-Exposed (Time Varying)' strategies (Section 9.2). In addition, separate summary display tables may be produced for the two study cohorts). The list of the planned data displays for each analysis population is provided in Appendix 11 (Section 9.11).

Description of the statistical methods to be used to minimize selection bias and confounding bias of safety analysis is also presented.

## 4. ANALYSIS POPULATIONS

### 4.1. Study analysis population

Population	Definition / Criteria	Analyses Evaluated
Enrolled	
 
All subjects who were enrolled irrespective of whether they meet the inclusion/exclusion criteria
 
	
 
Study Progress
 

Eligible	
 
Subjects in the 'Enrolled' population who met the inclusion/exclusion criteria [1]
 
	
 
Study Population
 
Other Covariates
 

Evaluable [3]	
 
Subset of the 'Eligible' population with a collection of enrollment data and at least 1 post-baseline assessment
 
	
 
Safety
 
Effectiveness
 

Sensitivity Analysis		
Sensitivity	
 
Subjects in the 'Enrolled' population who are on combination of medications that include both anti-malarials and corticosteroids, or who are in the 'Eligible' population [2]
 
	
 
Study Population
 

Evaluable Sensitivity [3]	
 
Subset of the 'Sensitivity' population with a collection of enrollment data and at least 1 post-baseline assessment
 
	
 
Safety
 

Refer to Appendix 11: List of Tables, Listings and Figures (TLF) Data Displays for details of the population used for each analysis endpoint.

[1] Based on medications reported in the SLE medications page and/or baseline corticosteroids page of the eCRF. In the SDTM data, eligible subjects who are taking Benlysta at enrollment (refer to section 9.5.2 for more details) will be assigned study exposure group = BENLYSTA. Subjects on immunosuppressants other than Benlysta at enrollment will be assigned exposure group = NON-BENLYSTA. Subjects who are only on anti-malarials or steroids at enrollment will not be included in any analyses. Moreover subjects who are on combination of medications at enrollment that include both anti-malarials and corticosteroids, but not immunosuppressants, will not be included in the 'Eligible' population.

**Note for programming:** some medications recorded as "Other" in CRF are immunosuppressants and should be considered when confirming eligibility. The manual review and selection of immunosuppressants reported as free text in "Other" field is under the responsibility of the GSK clinical team. At each data cut, review of new medications will manually be done and reported in an external Excel file.

[2] Compared to the 'Eligible' population, the 'Sensitivity' population will also include subjects on combination of medications that include both anti-malarials and corticosteroids, without immunosuppressant at enrollment. These subjects will be assigned exposure group = NON-BENLYSTA and used only for a sensitivity analysis.

[3]. **Note for programming:** subjects are considered 'Evaluable' if i) study day > 91 and visit is not end of study or ii) if previous point is not satisfied, last date of Adverse Events, Hospitalization and Concomitant Medications datasets is "day > 1" and Exposure dataset "day > 4". If previous point is not satisfied, the last contact date (as defined in Section 9.5.3) > 91 will be considered.

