5.1 Inclusion Criteria

Patients enrolled in the registry must meet the following inclusion criteria:

1. Males or females age 18 or older.
2. Have a clinical diagnosis of active SLE.
3. Current or history of autoantibody-positive SLE.
4. Must be treated with SLE therapy including BENLYSTA and/or immunosuppressants (eg, azathioprine, methotrexate, cyclophosphamide, mycophenolate, and biologics).
5. Have the ability to understand the requirements of the study, provide written informed consent, including consent for the use and disclosure of research-related health information, and comply with the study data collection procedures.

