Appendix 7 Potential Confounders for Malignancies and/or Infections List

- **Demographic and other general characteristics**
 - Age
 - Gender
 - Weight
 - Height
 - Race/ethnicity
 - Smoking history
 - Family history of cancer – first degree relatives & grandparents
 - Alcohol history
 - Female only:
 - Parity
 - Hormonal status

- **SLE disease profile**
 - Age at diagnosis
 - Organ involvement (SLEDAI 2000 Domains)
 - Disease Severity (SLEDAI 2000)
 - Organ Damage (SDI)
 - ANA status
 - Anti-dsDNA status
 - Quantitative Immunoglobulins (IgG, IgA, IgM)
 - Complement levels (C3/C4)
 - Total white blood cell count
 - Neutrophil differential %
 - Lymphocyte differential %

- **SLE treatment**
 - Name and duration of current SLE medications: including anti-malarials, biologics, steroids, and immunosuppressants at baseline
 - In addition, for steroids add dose

- **Co-morbidities**
 - ESRD/dialysis
 - Hepatitis B
 - Hepatitis C
 - HIV
 - Sjogren's Syndrome (Secondary)
 - Neutropenia
 - Post-transplant (any transplant)
 - Diabetes
 - Splenectomy

GlaxoSmithKline group of companies

- Chronic lung disease
 - Known immunoglobulin deficiencies
 - Tuberculosis (latent or active)
 - History of cancer (including NMSC)
 - History of serious infection
-
- **Vaccinations**
 - BCG
 - Pneumococcal
 - Influenza vaccine
 - Human papillomavirus (HPV)
 - Hepatitis
 - Varicella zoster
 - Any live vaccine received 30 days prior to enrollment

Signature Page for 116543 TMF-14148167 v2.0

Reason for signing: Approved	Name: PPD Role: A Date of signature: 25-May-2022 14:05:04 GMT+0000
------------------------------	--

Reason for signing: Approved	Name: PPD Role: A Date of signature: 25-May-2022 14:10:27 GMT+0000
------------------------------	--

Signature Page for TMF-14148167 v2.0

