#### **7.3.1.1.2. Positivity**

The positivity assumption specifies that every subject has a probability  $> 0$  to receive either treatment, otherwise no causal inference would be possible. The assumption of positivity will be checked by examining the overlap of the propensity score distribution for both treatment groups graphically. The SAS option WCLOUD will be used within the CAUSALTRT procedure to display weights, and if weights  $> 10$  are observed, the potential for non-positivity will be investigated (see section 7.3.1.4).

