## 9.9. Appendix 9: Treatment Propensity Score Models Covariates

**Table 4: Treatment Propensity Score Models Covariates**

Variables	Categories/Units	Key covariates*
Year of entry in the study	2013/2014 2015/2016 2017/2018 2019/2020	
Age at baseline	Years	Yes
Sex	Female Male	Yes
BMI	Underweight (<18.5) Normal (18.5 - <25) Overweight (25 - <30) Obese (30 - <40) Extremely obese (>=40)	
Race	Black White Asian Other	Yes
Ethnicity	Hispanic/Latino Not Hispanic/Latino	
Region	US/Canada Europe Other	Yes
Baseline Clinical SLEDAI 2000 score	Score	Yes
Baseline SDI	Score	
SLE duration since diagnosis	Years	
Used corticosteroids for SLE in the past six months	Yes No	Yes
Cardiovascular risk factors	Yes No	
Allergic reactions	Yes No	
Interstitial lung disease	Yes No	
Chronic Obstructive Pulmonary Disease (COPD)	Yes No	
Opportunistic Infection	Yes No	

Variables	Categories/Units	Key covariates*
Any other infection	Yes No	
Autoimmune disorders	Yes No	
Hypogammaglobulinaemia	Yes No	
Cancer	Yes No	
Non-Melanoma Skin Cancer (NMSC)	Yes No	
Family history of cancer	Yes No	
End stage renal failure	Yes No	
Depression and/or anxiety disorder	Yes No	
Suicidal ideation and/or suicidal depression and/or suicidal behavior	Yes No	
Attempted suicide	Yes No	
Dialysis	Yes No	
Transplant	Yes No	
Splenectomy	Yes No	

Treatment propensity score models covariates are collected at baseline.

\* Key covariates will be included in PS models. They are selected based on clinical judgment. If during building the PS model, there is a need to simplify the model specification, retention of key variables will be given priority. Any model simplification involving removal of these key covariates, will require further discussions and alignment with study team prior to implementation.

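### In the weighted analysis every comparator is on an immunosuppressant by rule while BENLYSTA patients need not be, and the propensity model has no term that could show it

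*SAP*

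**What the plan says.** - **Entry.** Protocol 5.1, criterion 4: "Must be treated with SLE therapy including BENLYSTA and/or immunosuppressants". BENLYSTA alone is enough. The examples of immunosuppressants given there include biologics.
- **Group assignment.** SAP 4.1 note [1] provides that "eligible subjects who are taking Benlysta at enrollment (refer to section 9.5.2 for more details) will be assigned study exposure group = BENLYSTA", with no condition on other drugs. For the comparator the rule is "Subjects on immunosuppressants other than Benlysta at enrollment will be assigned exposure group = NON-BENLYSTA". Patients taking both an antimalarial and a corticosteroid, "but not immunosuppressants, will not be included in the 'Eligible' population". They return only in the Sensitivity populations, as NON-BENLYSTA.
- **Weighted analysis.** SAP 7.3.1 and every propensity table in SAP 9.11.4 use the Evaluable population, a subset of Eligible.
- **Covariates.** The only SLE drug entry in SAP Table 4 is "Used corticosteroids for SLE in the past six months".
- **Checks.** SAP 7.3.1.1.2: "The assumption of positivity will be checked by examining the overlap of the propensity score distribution for both treatment groups graphically", with a further look if weights exceed 10. SAP 7.3.1.2.2 judges the balance produced by the model mainly on standardized mean differences (SMDs), with 0.1 as the benchmark.
- **Protocol commitments.** Appendix 7 lists as potential confounders "Name and duration of current SLE medications: including anti-malarials, biologics, steroids, and immunosuppressants at baseline". Section 8.3.2 says safety analyses will be adjusted for the Appendix 7 factors. It also promises subgroups by immunosuppressant use (yes/no; mycophenolate against other). It further promises a comparison of BENLYSTA initiators with comparators who start or switch an immunosuppressant and have similar background treatment.
- **What the SAP carries over.** SAP 5.6.1 keeps baseline immunosuppressant use as a descriptive covariate. The safety tables in SAP 9.11.2 include no display by immunosuppressant use. Their initiator tables are unweighted and not aligned on background treatment. SAP 2.1.1 nevertheless reports no change of approach beyond small modifications, and lists only the split of the two infection categories.

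**The concern.** The SAP names positivity as a condition for valid inverse probability weighting. Here the rules that form the groups create a stratum, patients on no immunosuppressant, that has no comparators at all. Weighting can rebalance strata that both groups occupy, but it cannot supply comparators to an empty one. Because the score omits the variable, the planned diagnostics can look clean while the groups differ on it.

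The protocol's sample size section describes belimumab added to standard care against standard care by itself. What the weighted tables would estimate is BENLYSTA with or without an immunosuppressant against an immunosuppressant. Protocol 1.1 associates immunosuppressive drugs with more infections in SLE. Lighter background immunosuppression in the BENLYSTA group would therefore tend to lower its infection rate for reasons unrelated to BENLYSTA. That is an awkward direction of error for a safety registry.

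**Working it through.** **1. The structural zero.** Let IS mean at least one non-BENLYSTA immunosuppressant at enrollment.
- Comparator in Evaluable: P(IS = yes) = 1, from SAP 4.1.
- BENLYSTA in Evaluable: P(IS = yes) = 1 − f, where f is not restricted by Protocol 5.1 or SAP 4.1.
- Hence P(BENLYSTA | IS = no) = 1 whenever f > 0.

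**2. Can the planned checks see it?** The SMD on IS is f / √(f(1 − f)/2). At f = 1% it is 0.01 / √(0.01 × 0.99 / 2) = 0.14, already above 0.1. But IS is not in Table 4, so this SMD is not among those reported.

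A simulation shows the mechanism (3,000 patients, 2:1, four synthetic covariates, stabilized weights from a score without IS, f assumed):

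| f | Largest weight | Largest modelled absolute SMD | Weighted IS use, BENLYSTA / comparator | Absolute SMD on IS |
|---|---|---|---|---|
| 20% | 2.9 | 0.013 | 78% / 100% | 0.76 |
| 30% | 2.6 | 0.015 | 69% / 100% | 0.95 |
| 40% | 3.1 | 0.012 | 58% / 100% | 1.20 |

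Scores overlapped, at about 0.3 to 0.9 in both groups. Every planned check passes.

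**3. Would adding IS to Table 4 be enough?** No. The logistic fit quasi-separates: it was singular at f = 20% and did not converge at 30% and 40%. SAP 7.3.1.2.1 then allows the covariate that causes non-convergence to be removed. The weight flag would not help either. A BENLYSTA patient off IS has a score near 1, so the stabilized weight is about (2/3)/1 = 0.67, far below 10.

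**4. The plan's own precision.** Person-years = N × (1 − 0.9⁵)/(−ln 0.9), which gives 7,773.5 and 3,886.8 (stated 7,773 and 3,886). The serious infection half-width is 1.96 × √(0.058 × (1/7,773 + 1/3,886)) × 100 = 0.93, as in Protocol Table 8-1.

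**5. Illustrative size for serious infection.** From the documents: R = 5.80 per 100 patient-years. Assumed:
- f is 20% to 60%;
- the rate ratio RR for IS use is 1.3 to 2.0;
- BENLYSTA has no true effect;
- all else is balanced;
- R applies to the all-IS comparator.

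The spurious difference is −R × f × (1 − 1/RR):
- f = 0.2, RR = 1.3: −5.80 × 0.2 × 0.231 = −0.27
- f = 0.4, RR = 1.5: −5.80 × 0.4 × 0.333 = −0.77
- f = 0.6, RR = 2.0: −5.80 × 0.6 × 0.5 = −1.74

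**6. Precision after restriction to IS users.** BENLYSTA person-years become 7,773 × (1 − f). At f = 40% the serious infection half-width goes from 0.93 to 1.96 × √(0.058 × (1/4,664 + 1/3,886)) × 100 = 1.03, and the mortality half-width from 0.32 to 0.35. At f = 60% serious infection is 1.96 × √(0.058 × (1/3,109 + 1/3,886)) × 100 = 1.14. These figures ignore the variance added by weighting and are for initiators and current users together.

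**The case against.** - **The contrast may be regimen against regimen.** The entry criterion accepts either drug type. If the question is BENLYSTA, with or without an immunosuppressant, against an immunosuppressant, then immunosuppressant use is part of the regimen and needs no overlap. That reading is coherent, but the SAP does not adopt it. The protocol's description of the cohorts and its Appendix 7 point the other way. What stands is that the contrast must be stated.
- **The Sensitivity populations include comparators without immunosuppressants.** This is correct, and adverse events of special interest (AESI) are tabulated in Evaluable Sensitivity (for example Tables 24.1101 and 24.1201). Those tables are unweighted, so they do not repair the weighted analysis.
- **The imbalance will be visible.** Tables 14.100 and 14.200 and Figure 1.000 describe baseline medication. They feed no propensity decision.
- **The analysis is descriptive and residual confounding is acknowledged.** Both are true, and they limit the consequence. But this factor is collected and named in the protocol, so it is not an unmeasured confounder.
- **Restriction can itself bias.** In BENLYSTA current users, being off an immunosuppressant at enrollment may follow from earlier BENLYSTA. Restricting then conditions on a post-treatment variable and may select patients who still need both. This stands, and it shapes the fix.

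**Conclusion.** The point holds for the weighted analysis in the Evaluable population. If any BENLYSTA patient enrolled without another immunosuppressant, positivity fails by rule for that factor, and the listed diagnostics cannot show it. The SAP also leaves out the immunosuppressant subgroup and the matched-background initiator comparison promised in Protocol 8.3.2.

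Three stronger readings are not supported:
- *That no comparator in the study is free of immunosuppressants.* The Sensitivity populations contain such patients.
- *That BENLYSTA is made to look safer on every endpoint.* Protocol 1.1 supports the direction for infections. For malignancy, Protocol 1.3 voices concern, but the overall hazard ratio for any immunosuppressive drug in Protocol 1.1 is 0.82 (0.50 to 1.36). A raised risk is suggested only for hematological malignancy, particularly with a 5-year lag. The documents establish no direction for mortality or psychiatric events.
- *That the bias is known to rival the planned precision.* Only 5.80 comes from the documents, and it is a pooled belimumab and placebo trial rate. The share off immunosuppressants and the rate ratio are assumptions. The middle case (−0.77) lies inside ±0.93, and −1.74 needs both extremes together.

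The sponsor should act on this before the weighted rates are interpreted, because the remedy is cheap and the protocol already commits to something close to it.

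**What to change.** 1. Add to SAP 7.3.3 and Appendix 11 a weighted analysis, under ITT and While On Initial Exposure, restricted in both groups to subjects on at least one non-BENLYSTA immunosuppressant at baseline. Refit the propensity model in that subset with immunosuppressant class (mycophenolate against other) as a covariate. Report the result beside the full-population one.
2. Present it for treatment initiators as the cleaner version, in line with Protocol 8.3.2. Present it for all subjects with a caution that in BENLYSTA current users immunosuppressant use at enrollment may be affected by earlier BENLYSTA.
3. State in SAP 7.3 that the full-population weighted contrast is BENLYSTA with or without an immunosuppressant against an immunosuppressant.

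Cost: two strategies in two populations make four rate tables, plus balance displays for the refitted models, all from medication data already collected at enrollment (Protocol 6.1). The downsides are wider intervals, more so in initiators, and possible selection among current users.

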## 4.2. Protocol Deviations

Protocol deviations will be tracked by the study team throughout the conduct of the study in accordance with the Protocol Deviation Management Plan (PDMP) [22 April 2024 Version 5.0]. If the PDMP is updated, the most current version of the PDMP will be used.

Data will be reviewed on an ongoing basis and prior to locking the database to ensure all important deviations are captured and categorized in the protocol deviations dataset. This dataset will be the basis for the table and listing of protocol deviations.

A summary of subjects who did not meet inclusion/exclusion criteria will also be provided.

## 5. CONSIDERATIONS FOR DATA ANALYSES AND DATA HANDLING CONVENTIONS

### 5.1. Study Exposure & Sub-group Display Descriptors

Exposure Group Descriptions			
Study Exposure Group		Data Displays for Reporting	
Code	Description	Description	Order in TLF
A	BENLYSTA	BENLYSTA	2
B	NON-BENLYSTA	NON-BENLYSTA	1

Exposure group comparisons will be displayed using the following specified descriptors:

- BENLYSTA vs NON-BENLYSTA

BENLYSTA group is used for subjects who are exposed to Benlysta while NON-BENLYSTA group is used for subjects who are not exposed to Benlysta. For summary description of baseline characteristics, the exposure group represents subjects' exposure at enrollment (i.e 'Initial Exposure'). For summary of safety and effectiveness endpoints, the exposure group will be defined using the 'Initial Exposure', 'As-Exposed', and/or 'Ever-Exposed' strategies (see Appendix 2, Section 9.2). 'As-Exposed' is defined based on whether or not a subject is using Benlysta at specific period during the study follow-up time; thus a subject's exposure group can change over time depending on switching to or off Benlysta. 'Ever-Exposed' is defined based on whether a subject was exposed to Benlysta at any point in time after enrollment, in this instance a subject's exposure can change only once over time if they were initially 'Unexposed' and then started using Benlysta; once a subject is exposed to Benlysta, they will always be considered as 'Exposed'.

The specific strategy for defining exposure group and the analysis approach for accrued data will be indicated on the TLFs titles and list of the planned data displays provided in Appendix 11 (Section 9.11).

---

 Subjects are considered to have switched from BENLYSTA exposure group if they permanently discontinued Benlysta treatment or missed doses of Benlysta for more than 98 days and do not restart doses of Benlysta on or before day 99 after the last Benlysta medication end date. Subjects are considered to have switched from NON-BENLYSTA exposure group if they initiate or start receiving Benlysta dose anytime during the study follow-up period. Change of different study-qualifying Non-Benlysta Standard of Care (SOC) medications does not count as exposure switching.

Primary analysis will be done on ‘Initial Exposure’ strategy for all endpoints while ‘As--Exposed’ and ‘Ever-Exposed’ will apply for some endpoints as exploratory analysis:

Endpoints	Primary analysis		Exploratory analysis	
	Initial Exposure Intent-To-Treat (ITT)	While on Initial Exposure	As-Exposed Time varying*	Ever-Exposed
Primary endpoints (AESI)				
Serious Psychiatric events	Y	Y	Y1, Y2	
Serious infections, opportunistic infections and other infections of interest	Y	Y	Y1, Y2	
NMSC and malignancies excluding NMSC	Y	Y	Y1	Y
Mortality	Y	Y	Y1, Y2	Y
Effectiveness endpoints				
SLICC/ACR Damage index (SDI)	Y			
Concomitant SLE medications including steroids	Y			
Hospitalization	Y	Y	Y1	

\* For As-Exposed strategy, 14 weeks risk window or 6-months risk window are defined depending on the endpoint (see Appendix 2, Section 9.2). Y=Yes. Y1 = applicable to the 14 weeks risk window, Y2 = applicable to the 6-months risk window.

For some display Tables and Figures, the ‘Total’ for the two exposure groups combined may be presented, as shown on the TLFs mock-shell (Appendix 12). The format of Graphs/Figures will follow the graphical display standard and handling convention specified in Appendix 4Appendix 5.

The "Initial Exposure" strategy will be used to derive weights from the Propensity Scores model for the weighted analyses (see section 7.3). This exposure includes two different analysis approaches:

- ‘Intent-To-Treat (ITT)’ and
- ‘While On Initial Exposure’.

Other subgroups will be described in more detail in Section 5.6.2.

